## 1.2 Safety of repeated HP C pyruvate injections

There is ample evidence from pre-clinical studies and from the known short half-life of pyruvate metabolism to support the safety and feasibility of this approach. Specifically, hundreds of IUCAC approved pre-clinical C MRI studies (mice, rats and canines) at UCSF have used multiple injections of hyperpolarized [1-C]pyruvate within the same imaging study without evidence of adverse events. The SPINIab DNP polarizer, used in patient studies, allows for up to 4 samples to be polarized and dissolved in rapid succession. We have shown in a rat model that minimal perturbations occurred in pyruvate metabolism as a result of 4 injections of hyperpolarized [1-C]pyruvate injected in 5 minute intervals (6). Moreover, two injections of hyperpolarized [1-C]pyruvate have already been approved and performed in over 20 human studies at UCSF (CHR#13-12719, CHR 17-24246). These studies have demonstrated the safety of serial injections without any adverse effects noted.

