#### 6.3.2 Treatment Period

#### 6.3.2.1 Study Procedures, Baseline HP C pyruvate MRI

- Pre-Scan
  - Clinical Assessments
    - Vital signs including blood pressure and heart rate

Before vital signs are measured, the subject should be resting for at least 5 minutes (if possible). The same position will be used each time vital signs are measured for a given subject and blood pressure will be measured from the arm contra-lateral to the site of IMP administration whenever possible.

• Standard MR Scan

Patient is transferred to the MRI suite. Standard 1H MRI exam will be obtained in the abdomen, including T2 weighted imaging, and T1 weighted imaging pre and dynamically following gadolinium contrast administration (gadobutrol at 0.1ml/Kg body weight). If the patient has estimated glomerular filtration rate (eGFR) < 30, gadobutrol will not be administered.

- HP C MR Imaging
  - Study Tx / Drug Admin: Hyperpolarized 13C pyruvate injection

Hyperpolarized 13C pyruvate will be injected intravenously at a dose of 0.43 mL/kg and at a rate of 5 mL/second followed by a 20 mL saline flush at 5 mL/second. The volume to be injected is based upon body weight and is outlined in Appendix 2.

- Imaging Procedures: Dynamic 13C MR imaging
  - 1-2 minutes post-injection
  - 13C 3D MRI sequence with Multiband spectral-spatial excitation pulse for minimal [1-13C] pyruvate saturation and echo-planar imaging (EPI) readout for accelerated spectral-spatial sampling.
  - An optional second HP 13C pyruvate injection and MRI acquisition will be performed within 15 to 60 minutes following completion of the first scan. This repeat injection and scan is optional. This second injection will only occur if there is no adverse reaction to the first injection. The optional second injection and MRI scan are used to assess the repeatability of tumor HP 13C pyruvate metabolism.

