### 8.3.3 Secondary Analysis

Cohort A and B: Repeatability of C pyruvate metabolism measures in the target tumor (primary tumor and/or abdominal metastasis) in patients with same-day repeated dose.

Cohort B: The association between the baseline or changes in the target tumor pyruvate metabolism at 4 weeks post treatment initiation and tumor best objective response as defined according to RECIST criteria on subsequent standard-of-care CT.

Secondary endpoint analysis: For Cohort A and B, intraclass correlation coefficient (ICC) will be used to estimate the intra-subject agreement to assess repeatability of tumor HP C pyruvate metabolism in patients with same-day repeated dose.

ICC will be used to estimate agreement, and obtained from a one-way analysis of variance model based on 2 measurements per subject. The result will be presented with a 95% confidence interval. If 20 (out of 40) subjects had repeated dose of the hyperpolarized 13C pyruvate, we will have 90% power to show an ICC of at least 0.6.

For Cohort B, tumor best objective response will be defined using RECIST 1.1 on subsequent clinical CT scans. For the purpose of response assessment in this pilot study, we will group patients either as having disease control when the best response is complete response (CR), partial response (PR), or stable disease (SD) on subsequent clinical CT scans, or having disease progression when the best response is progressive disease (PD) on subsequent CT scans. Based on prior published studies (37, 38) in PDA patients who receive first- or second-line therapies (i.e. FOLFIRINOX, gemcitabine plus nab-paclitaxel, or gemcitabine monotherapy), we estimate an average 50% disease control rate for this group of patients. We will compare the baseline or changes in the target tumor C pyruvate metabolism at 4 week (+/-2 weeks) after treatment initiation between the disease control group and disease progression group (as defined by RECIST on subsequent clinical CT scans) using the Mann-Whitney tests.

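### Section 8.3.3 summarises same-day repeatability only by a one-way ICC, which does not show whether a lowered value comes from a systematic second-scan shift or from random scan error

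*Combined protocol and SAP*

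**What the plan says.** Section 8.3.3 names the ICC as the repeatability analysis for both cohorts, "obtained from a one-way analysis of variance model based on 2 measurements per subject". On precision it adds: "The result will be presented with a 95% confidence interval". On size it says: "If 20 (out of 40) subjects had repeated dose of the hyperpolarized 13C pyruvate", then "we will have 90% power to show an ICC of at least 0.6". The null ICC, alpha and sidedness of that power statement are not given. No scan-order term, mean paired difference or limits of agreement is planned.

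Section 6.3.2.1 fixes the sequence. The optional second injection and acquisition "will be performed within 15 to 60 minutes following completion of the first scan", and only in patients with no adverse reaction to the first injection. Section 6.3.2.2 repeats this for the Cohort B follow-up visit. Both sections give repeatability as the purpose of the second scan.

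On whether one dose alters the next measurement, section 1.2 cites a rat model in which "minimal perturbations occurred in pyruvate metabolism as a result of 4 injections of hyperpolarized" pyruvate, given at 5-minute intervals. The human experience with two injections in that section is reported as safety, not as absence of a metabolic shift.

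**The concern.** A one-way model treats a patient's two measurements as interchangeable replicates. Here they are not: one always follows a full dose given earlier in the same session. If that dose moves the second measurement up or down by a consistent amount, the one-way model counts the movement as within-subject error.

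The two sources have different consequences. Cohort B's primary endpoint is the change between the pre-treatment and 4-week scans. A constant shift in second scans plays no part in comparing the first scan at one visit with the first scan at the other. Random scan error does, and a reader needs its size to judge whether an observed change exceeds measurement noise. If the planned ICC came out lower than hoped, the report would not show which explanation applied.

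**Working it through.** **Inputs.** From section 8.3.3: n = 20 patients with k = 2 scans, and a one-way model. From sections 6.3.2.1 and 6.3.2.2: fixed scan order. Assumed, because the documents give no value: the size of the shift, and an underlying ICC of 0.80 (0.60 as a second case).

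**Step 1: the plan's own figure.** For the one-way F test of ICC = 0 against ICC = 0.6, power = P(F(19, 20) > Fcrit / C), with C = (1 + 0.6)/(1 − 0.6) = 4.
- One-sided alpha 0.05: 91.1%, which reproduces the stated 90%.
- One-sided alpha 0.025: 84.8%, which does not.

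So the 90% holds under an unstated one-sided 0.05 test against zero. The present point does not dispute it.

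**Step 2: where a shift goes.** Let the between-patient variance be 1, the error variance e and the mean second-minus-first shift d. One patient's within-subject sum of squares is (difference)²/2, with expectation (2e + d²)/2. Hence:
- E(MSW) = e + d²/2
- E(MSB) = 2 + e
- one-way ICC = (MSB − MSW)/(MSB + MSW)

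**Step 3: assumed range at a true ICC of 0.80.** Here e = (1 − 0.80)/0.80 = 0.25, so the within-subject SD is 0.5 and E(MSB) = 2.25.

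| Shift (within-subject SD) | d | E(MSW) | One-way ICC | Apparent within-subject SD, ratio to true |
|---|---|---|---|---|
| 0 | 0 | 0.250 | 2.000/2.500 = 0.80 | 1.00 |
| 0.5 | 0.25 | 0.281 | 1.969/2.531 = 0.78 | √1.125 = 1.06 |
| 1 | 0.50 | 0.375 | 1.875/2.625 = 0.71 | √1.5 = 1.22 |
| 1.5 | 0.75 | 0.531 | 1.719/2.781 = 0.62 | √2.125 = 1.46 |

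**Step 4: simulation with 20 pairs (40,000 replicates), mean estimates for shifts of 0 / 0.5 / 1 / 1.5 within-subject SD.**
- True ICC 0.80: one-way 0.78 / 0.76 / 0.70 / 0.60; two-way absolute agreement 0.78 / 0.76 / 0.71 / 0.64; two-way consistency 0.78 throughout.
- True ICC 0.60: one-way 0.58 / 0.54 / 0.43 / 0.29; absolute agreement 0.58 / 0.55 / 0.49 / 0.41; consistency 0.58 throughout.

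With no shift, the three indices have the same mean. With a shift, only the version that removes the order effect still reflects random error alone.

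**Step 5: can 20 pairs show the shift?** The standard error of the mean difference is √(2e/20). At e = 0.25 this is √0.025 = 0.16, or 0.16/0.5 = 0.32 within-subject SD. A shift of 1 within-subject SD therefore gives t of about 0.5/0.158 = 3.2. In the simulation, a two-sided 5% paired t-test detects shifts of 0.5, 1 and 1.5 within-subject SD about 32%, 85% and 99% of the time.

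**Step 6: cost of an order term.** Error degrees of freedom fall from n(k − 1) = 20 to (n − 1)(k − 1) = 19. Power for ICC 0.6 against 0 becomes 90.4% at one-sided 0.05 (from 91.1%), or 83.7% at one-sided 0.025 (from 84.8%).

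**The case against.** The strongest reply is that section 8.3.3 sets out to estimate agreement. For agreement, a systematic second-scan shift is disagreement and ought to lower the index. The one-way ICC does that and errs conservatively, since a shift cannot make repeatability look better than it is. This stands: the planned analysis is incomplete in what it reveals, not wrong.

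The cited evidence also points towards a small shift. Four injections 5 minutes apart in rats is a denser schedule than two injections with at least 15 minutes after the first scan. At half a within-subject SD the expected ICC falls only from 0.80 to 0.78. That is small beside the sampling error: an observed ICC of 0.6 from 20 pairs would have a 95% CI of about 0.23 to 0.82. This also stands, although rat data do not exclude a shift in patients.

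A reader might infer three stronger things that the documents do not support.
- That the plan would report poor repeatability. At a true ICC of 0.80, even shifts of 1 and 1.5 within-subject SD leave expected values of 0.71 and 0.62, above 0.6, the only ICC value the plan names.
- That shifted second scans would contaminate the primary analysis by being pooled with first scans. Nothing in section 8.3 plans such pooling, and sections 6.3.2.1 and 6.3.2.2 tie the second scan to repeatability.
- That the two sources can never be told apart. The data record scan order, so the limit lies in the planned summary and not in the design.

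**Conclusion.** The point holds as a cheap improvement to a secondary analysis in a pilot study. Scan order is fixed, the only planned summary has no order term, and a mean shift d enters the within-subject mean square as d²/2 without being visible in the output.

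The size depends on assumed shifts. At a true ICC of 0.80, the one-way ICC falls to about 0.78, 0.71 and 0.62 for shifts of 0.5, 1 and 1.5 within-subject SD. If the true shift is near zero, as the rat data suggest, the practical effect is negligible and the added output would simply document that. The figures also rest on the plan's own supposition of 20 patients accepting the optional second dose. Prespecifying the separation is better than explaining a low ICC after the fact.

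**What to change.** In section 8.3.3, for each of the three metabolism measures:
1. Report the mean second-minus-first difference with its 95% CI.
2. Obtain the ICC from a two-way model with patient random and scan order fixed. Report the absolute-agreement ICC with its 95% CI as the repeatability index.
3. Report the within-subject SD with the order effect removed (or the consistency ICC), as the measure of random scan error relevant to change between visits.

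The cost is one error degree of freedom, less than one percentage point of power at one-sided 0.05 (about 91.1% to 90.4%), and a few more lines of reporting. No additional patients, injections or scans are needed. With 20 pairs, the interval for the mean difference would be informative about a shift near one within-subject SD, but would often not resolve one of half that size. The report should therefore show the interval and not only a test result.

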## 3 Study Design

#### 3.1 Characteristics

This is a pilot prospective study to investigate the utility of HP C pyruvate MRI for assessing metabolism and monitoring early treatment response in patients with locally advanced or metastatic PDA. Patients will be enrolled in parallel in one of two cohorts:

Cohort A (N=20): Patients with locally advanced or metastatic PDA who are already on therapy will undergo hyperpolarized (HP) C pyruvate MRI at a single time-point.

Cohort B (N=20): Patients with locally advanced or metastatic PDA will undergo HP C pyruvate MRI at baseline prior to the initiation of a new line of therapy (standard-of-care first- or

second-line systemic therapies, radiotherapy, or therapies as part of a clinical trial), and again at 4 weeks (+/- 2 weeks) following treatment initiation.

In both Cohort A and B, patients may undergo an optional second dose of C pyruvate injection followed by MRI during the same imaging session.

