## 6.3.2.2 Study Procedures, Follow-Up HP C pyruvate MRI (cohort B only)

For patients in Cohort B, a follow up HP 13C pyruvate MRI will be obtained as per above procedures at 4 weeks (+/- 2 weeks) following the initiation of systemic therapy or radiotherapy as per clinical care.

- Pre-Scan
  - o Clinical Assessments
    - Vital signs including blood pressure and heart rate

Before vital signs are measured, the subject should be resting for at least 5 minutes (if possible). The same position will be used each time vital signs are measured for a given subject and blood pressure will be measured from the arm contra-lateral to the site of IMP administration whenever possible.

Standard MR Scan

Patient is transferred to the MRI suite. Standard 1H MRI exam will be obtained in the abdomen, including T2 weighted imaging, and T1 weighted imaging pre and dynamically following gadolinium contrast administration (gadobutrol at 0.1ml/Kg body weight). If the patient has estimated glomerular filtration rate (eGFR) < 30, gadobutrol will not be administered.

- HP C MR Imaging
  - o Study Tx / Drug Admin: Hyperpolarized 13C pyruvate injection

Hyperpolarized 13C pyruvate will be injected intravenously at a dose of 0.43 mL/kg and at a rate of 5 mL/second followed by a 20 mL saline flush at 5 mL/second. The volume to be injected is based upon body weight and is outlined in Appendix 2.

- Imaging Procedures: Dynamic 13C MR imaging
  - 1-2 minutes post-injection
  - 13C 3D MRI sequence with Multiband spectral-spatial excitation pulse for minimal [1-13C] pyruvate saturation and echo-planar imaging (EPI) readout for accelerated spectral-spatial sampling.
  - An optional second HP 13C pyruvate injection and MRI acquisition will be performed within 15 to 60 minutes following completion of the first scan. This repeat injection and scan is optional. This second injection will only occur if there is no adverse reaction to the first injection. The optional second injection and MRI scan are used to assess the repeatability of tumor HP 13C pyruvate metabolism.

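### The repeatability ICC uses one same-day pair per patient, but Cohort B patients may have two; the plan leaves the second pair unused and does not say which pair counts.

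*Combined protocol and SAP*

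**What the plan says.** Section 3.1 offers the repeat to everyone: "In both Cohort A and B, patients may undergo an optional second dose of" the agent in the same imaging session. Cohort A has one imaging visit. Cohort B has two, one before the new therapy and one about 4 weeks after it starts. Section 6.3.2.1 (baseline) and Section 6.3.2.2 (Cohort B follow-up) each contain the option and give the same purpose for it: "The optional second injection and MRI scan are used to assess the repeatability of tumor HP 13C pyruvate metabolism".

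Section 8.3.3 specifies one ICC for both cohorts, "to estimate the intra-subject agreement to assess repeatability of tumor HP" pyruvate metabolism in patients with a same-day repeat. It comes from a one-way analysis of variance "based on 2 measurements per subject". On precision: "The result will be presented with a 95% confidence interval". On power: "If 20 (out of 40) subjects had repeated dose of the hyperpolarized 13C pyruvate", then "we will have 90% power to show an ICC of at least 0.6".

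Nothing in Section 8.3 says which visit's pair enters the ICC, or what to do when a patient has a pair at each visit. The general sentence that data from all dosed subjects are included when appropriate does not settle it.

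**The concern.** A Cohort B patient who accepts the repeat at both visits has four scans in two same-day pairs, with a treatment start between them. The model has room for two of the four. The analyst must then choose a pair after the data exist, or depart from the text to use the rest.

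Repeatability is a secondary objective. It also helps in reading the Cohort B primary endpoint, because a 4-week percent change means little unless it exceeds scan-to-scan noise. The second injection at follow-up is given for repeatability, and the analysis section assigns its data no role once a patient already has a baseline pair.

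**Working it through.** **1. The plan's own power figure.** Inputs from Section 8.3.3: n = 20 subjects, k = 2 measurements, ICC 0.6. The null value, alpha and sidedness are not stated. I assume null ICC 0 and one-sided alpha 0.05. The one-way F test rejects when MSB/MSW exceeds F(0.95; 19, 20) = 2.137. At ICC 0.6 the ratio is scaled by 1 + 2 x 0.6/0.4 = 4, so power = P(F(19, 20) > 2.137/4 = 0.534) = 91.1%. This agrees with the stated 90%. At two-sided 0.05 it would be 84.8%. The figure therefore fits one pair per subject.

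**2. How many pairs are possible.** Cohort A: 20 x 1 = 20. Cohort B: 20 x 2 = 40. The total is up to 60, of which one pair per subject uses at most 40. The documents give no expected number of patients repeating at both visits. For illustration I assume 20 patients with a repeat, 10 of them with two pairs: 10 + 2 x 10 = 30 pairs.

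**3. Precision lost by using one pair each.** With m pairs and same-day differences d, the within-session variance is the sum of d² divided by 2m, on m degrees of freedom. Patient and visit effects cancel in d, so two pairs from one patient can both be used here. This assumes the same within-session variance at both visits. The 95% limits are the SD times √(m/χ²).

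| Pairs m | χ² 0.975 and 0.025 points | Multipliers of the SD |
|---|---|---|
| 20 | 34.17 and 9.59 | 0.77 to 1.44 |
| 30 (assumed) | 46.98 and 16.79 | 0.80 to 1.34 |

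For an observed ICC of 0.6, the exact 95% interval is 0.23 to 0.82 with 20 pairs. With 30 fully independent pairs it would be 0.32 to 0.79. That is a best case, because a patient's two pairs are correlated.

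**4. What the alternatives to one pair would do.** Assumed variances: subject 0.7, visit within subject 0.1, within session 0.2, with a shift of 0.5 at follow-up. The true same-day ICC is (0.7 + 0.1)/1.0 = 0.80.

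If a two-pair patient's four scans are entered as plain repeats, the expected within-subject sum of squares is 2 x 0.2 (within sessions) + (2 x 0.1 + 0.2 + 0.5²) (between visits) = 0.40 + 0.65 = 1.05 on 3 degrees of freedom. The mean square is 0.35 instead of 0.20, and the excess is visit-to-visit and treatment change. With 10 of 20 patients having two pairs, the overall mean square is (10 x 0.2 + 10 x 1.05)/(10 + 30) = 0.31. With 5 of 20 it is (15 x 0.2 + 5 x 1.05)/(15 + 15) = 0.28.

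Simulation with these inputs and 20 patients:

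| Handling | 10 of 20 with two pairs | 5 of 20 with two pairs |
|---|---|---|
| One pair per patient: mean ICC | about 0.78 | about 0.78 |
| One pair per patient: 95% CI coverage | about 95% | about 95% |
| Four scans pooled by patient: mean ICC | about 0.69 | about 0.72 |
| Pairs counted as separate patients: 95% CI coverage | about 93% | about 94% |

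The shortfall of the one-pair mean from 0.80 is small-sample bias. It is part of the gap in the pooled rows too.

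**The case against.** The analysis as written is sound. Two measurements per subject, in patients with a same-day repeat, means one same-day pair each, and that gives close to nominal coverage and the stated power. Counting a patient twice contradicts the per-subject wording. Pooling four scans contradicts both the number two and the same-day restriction. The second injection is optional and withheld after an adverse reaction to the first, so few patients may have two pairs, and a visit-within-subject variance would then be poorly estimated. Naming one pair in advance would settle the matter within the stated model.

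Most of this stands. A reader might infer that the planned model mishandles the follow-up pairs or yields a biased ICC. The documents do not support that: the biased results come only from handling that the text does not call for. A reader might also expect a larger fall from pooling. A mean of about 0.63 does arise if the whole sample is 10 patients who all have two pairs, but the plan's figure is 20 subjects, and in that smaller sample even one pair per patient averages only 0.76.

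What does not fall is that the plan collects pairs for repeatability that its only repeatability analysis does not use, and that it names no pair in advance.

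**Conclusion.** The point holds as a minor improvement. The literal plan is valid but does not use second pairs, and the choice of pair is open. Under the assumed 30 pairs against 20, the limits for the within-session SD tighten from x0.77–1.44 to x0.80–1.34. With fewer double repeats the gain shrinks, and with none it vanishes. A written rule also closes off pooling across treatment, which in the illustration would bring a true ICC of 0.80 down to a mean of about 0.69 or 0.72. It would likewise prevent double counting, which costs a point or two of coverage.

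These sizes rest on assumed variances, an assumed treatment shift and an assumed number of double repeats, none of which the documents give. It would be wrong to infer that the 90% power is overstated on this account: it is a one-pair-per-subject figure and it reproduces, given null ICC 0 and one-sided 0.05.

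**What to change.** In Section 8.3.3, estimate repeatability from all same-day pairs with a linear mixed model: visit as a fixed effect, and random effects for subject and for visit within subject. State how Cohort A's single on-therapy scan is coded in the visit factor. Report the same-day ICC, (subject + visit-within-subject variance)/total, and the within-session SD or CV, each with a 95% confidence interval. The SD or CV is the quantity to set against a 4-week change.

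Add a fallback. If too few patients have two pairs to fit the model, compute the one-way ICC from the first available pair per patient, and still pool all same-day differences for the within-session SD. Fix the criterion for falling back before the data are examined.

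The cost is SAP wording and a slightly more complex model whose visit-within-subject variance may be imprecise. No new data or visits are needed.

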## 8 Statistical Considerations and Evaluation of Results

#### 8.1 Sample Size Considerations

#### 8.1.1 Sample Size and Power Estimate

For Cohort A: Assuming signal-to-noise ratio of target tumor C pyruvate metabolism of 30 and standard deviation of 5, a sample size of 20 evaluable patients will provide an expected width of 95% confidence intervals of +/-2.2, with a standard error of 1.1.

For Cohort B: A sample size of 20 evaluable patients will allow the detection of a standardized difference of 0.38 with 80% power at a 2-sided significance level of 0.05 using a paired t-test.

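### Does the 90% power statement for the repeatability ICC in Section 8.3.3 promise more than 20 repeat-dosed patients can show?

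*Combined protocol and SAP*

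**What the plan says.** Repeatability of the tumour pyruvate measures in patients given a second injection on the same day is a secondary objective for both cohorts. Section 8.3.3 sets out the estimator: "ICC will be used to estimate agreement, and obtained from a one-way analysis of variance model based on 2 measurements per subject". It then says: "The result will be presented with a 95% confidence interval".

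The power statement is conditional: "If 20 (out of 40) subjects had repeated dose of the hyperpolarized 13C pyruvate", then "we will have 90% power to show an ICC of at least 0.6". The condition matters because Section 3.1 makes the repeat injection voluntary ("patients may undergo an optional second dose"), so 20 is a scenario for uptake and not a number fixed by design.

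Section 8.3.3 attaches no null value, assumed true ICC, significance level or sidedness to the 90%. Section 8.1.1, by contrast, gives the level, sidedness and test for Cohort B: "with 80% power at a 2-sided significance level of 0.05 using a paired t-test".

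**The concern.** A power figure needs a null value and an alternative, and this sentence supplies one number, 0.6. If 0.6 were both the true ICC and the threshold to be exceeded, the chance of showing an ICC above 0.6 would equal the test's alpha: 2.5% at the level of the planned interval, or 5% at one-sided 0.05. It could not be 90%.

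The most familiar calculation giving about 90% with 20 patients and two scans each tests ICC = 0 when the true ICC is 0.6. Success in that test shows that the ICC is above 0, which is much weaker than showing that it is at least 0.6. A reader relying on the sentence could expect the study to establish repeatability of 0.6 or better when the data might establish far less. This is also the plan's only statement of what the repeat-dose data can deliver.

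**Working it through.** **Inputs.** From Section 8.3.3: n = 20 patients, k = 2 measurements each, one-way ANOVA, ICC value 0.6, stated power 90%, and a 95% confidence interval. From Section 8.1.1: two-sided 0.05, stated for Cohort B only. The null ICC, the true ICC and alpha for the repeatability statement are not given, so each reading below is an assumption.

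**Formula.** Let F = MSB/MSW, with 19 and 20 degrees of freedom, and θ(ρ) = (1 + ρ)/(1 − ρ). For a null ρ₀ and a true value ρ₁, with F_crit the upper-tail critical value,

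power = P(F₁₉,₂₀ > F_crit × θ(ρ₀)/θ(ρ₁)).

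F_crit is 2.137 for an upper tail of 0.05 and 2.482 for 0.025. The latter matches the lower limit of a two-sided 95% interval. The values needed are θ(0) = 1, θ(0.6) = 4, θ(0.7) = 5.667, θ(0.8) = 9 and θ(0.9) = 19.

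**Reading 1: null 0, true ICC 0.6.**
- One-sided 0.05: P(F > 2.137/4 = 0.534) = 91.1%. A simulation of 200,000 runs gave 91.0%. With 19 patients the power is 89.8%, so 20 is the smallest number that reaches 90%.
- One-sided 0.025, the level of the planned interval: P(F > 2.482/4 = 0.621) = 84.8%.
- Smallest observed ICC that rejects at one-sided 0.05: (2.137 − 1)/(2.137 + 1) = 0.362. Its exact 95% interval is −0.07 to 0.69.

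The stated 90% therefore reproduces at one-sided 0.05. On this reading a positive result shows an ICC above 0 and no more.

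**Reading 2: literal wording, lower 95% limit above 0.6 (null 0.6, upper tail 0.025).**

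| True ICC | Cut-off, 2.482 × 4/θ | Probability |
|---|---|---|
| 0.7 | 1.752 | 11.1% |
| 0.8 | 1.103 | 41.4% |
| 0.9 | 0.523 | 91.8% |

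The stated 90% also reproduces here, at a true ICC of about 0.9 (0.895 gives 90%). The observed ICC would need to reach (4 × 2.482 − 1)/(4 × 2.482 + 1) = 0.817.

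**What the planned report will show.** For an observed ICC of 0.6, the lower limit comes from 4/2.482 = 1.612, giving (1.612 − 1)/(1.612 + 1) = 0.23. The upper limit comes from 4 × 2.509 = 10.036, where 2.509 is the upper 0.025 point with 20 and 19 degrees of freedom, giving (10.036 − 1)/(10.036 + 1) = 0.82. The interval is 0.23 to 0.82 whichever reading lay behind the 90%.

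**The case for a change.** The best case for rewording is that the sentence is defective on either reading. If the null was 0, it names the wrong conclusion. If the null was 0.6, it rests on an undisclosed true ICC near 0.9, and the probability falls to 41% at 0.8 and 11% at 0.7. Reading 1 also has some claim to be what was done. It needs only the numbers in the sentence plus the customary null of 0, and 20 is the smallest sample that reaches 90%. Rewording one sentence would cost almost nothing.

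Part of this stands: the assumptions should ideally have been written down, and a reader should not take the sentence as a promise that 0.6 will be exceeded.

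The stronger claim, that the sentence misdescribes its own figure, does not stand. Reading 1 needs a one-sided 0.05 level that appears nowhere in the documents; at the level of the planned interval it gives 84.8%. Reading 2 uses the documented 95% interval and takes the wording at face value, but needs a true ICC that the documents do not give. That 20 is the smallest sufficient number is weak evidence, because Section 8.3.3 introduces 20 as half of enrolment taking up an optional injection. Writing either test into the plan would attribute to the sponsor a choice that the documents do not record.

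**Conclusion.** The concern does not call for a change. The 90% is not miscalculated: it is within two percentage points under two different sets of assumptions (91.1% and 91.8%), and the documents do not say which applies. Under the first, the phrase "show an ICC of at least 0.6" is ordinary if loose shorthand for having that power when the true ICC is 0.6 or more. Under the second, it is literally correct, given a true ICC of about 0.9.

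What remains is missing detail in a supporting sentence, for a secondary endpoint of a 40-patient pilot. Followed as written, the plan yields the same one-way ANOVA ICC and the same 95% confidence interval on either reading. No hypothesis test of the ICC, success rule or enrolment target is tied to the 90%, and the number of repeat-dosed patients depends on voluntary uptake. The interval will tell readers what was established; an observed ICC of 0.6 in 20 patients would visibly be compatible with values from about 0.23 to 0.82. Stating the null, true ICC, alpha and sidedness would be tidier but would change no analysis or conclusion.

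These figures assume exactly 20 patients with two usable measurements each and the normal one-way random-effects model behind the F distribution.
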